3.3. Rationale for the Extension Phase

Once the end of the main study has been reached (Section 17.9.1), accommodation must be made to allow subjects benefiting from imetelstat to continue treatment, until there is loss of benefit or unacceptable toxicity, as determined by the investigator according to local standard of care. Subjects will be followed in the Extension Phase for at least 5 years from the first dose of imetelstat received in Part 2 of the main study (including treatment and follow-up), or 3 years of post-treatment follow-up from the last dose of study treatment, whichever occurs later, or until death, withdrawal of consent, study termination, or until a subject is lost to follow-up. Subjects receiving imetelstat in the QTc substudy may also enter the Extension Phase after the clinical cut off for the primary analysis is reached for the substudy. It is anticipated that the Extension Phase will allow sufficient time for all subjects to receive adequate treatment and for collection of long-term survival data, and additional maturity of the survival data for a more precise estimate of OS. It is also anticipated that during this time the rate of observed deaths will reach approximately

65%, indicating a mature data set. Because sufficient efficacy data will have been collected during the main study to allow the planned final analysis for the main study, data collection during the Extension Phase will be limited to imetelstat treatment information (exposure), transfusion collection, survival status, routine safety reporting, laboratory assessments for safety monitoring, and disease progression including progression to AML.

4. SUBJECT POPULATION

Subject eligibility will be reviewed and approved by the sponsor prior to C1D1 (Part 1) or Randomization (Part 2) (as defined in Section 3.1). Screening will be performed within 28 days prior to C1D1 (Part 1) or Randomization (Part 2).

The inclusion and exclusion criteria for enrolling subjects in this study are described in the following 2 subsections for Part 1 and main study of Part 2.

For subjects participating in the Ventricular Repolarization substudy after Protocol Amendment 7 (Part 2 only), the eligibility criteria are provided in Attachment 11.

If there is a question about the inclusion or exclusion criteria below, the investigator should consult with the appropriate sponsor representative before C1D1 (Part 1) or Randomization (Part 2). Waivers are not allowed.

NOTE: Investigators should ensure that all study enrollment criteria have been met at screening. The last laboratory result obtained prior to enrollment/randomization will be used to determine eligibility. If a subject's status changes (including laboratory results or receipt of additional medical records) after screening but before C1D1 (Part 1) or Randomization (Part 2) (as defined in Section 3.1) such that he or she no longer meets all eligibility criteria, then the subject should be excluded from participation until all eligibility criteria have been met (retesting information in Section 9.1.3). Section 17.4, Source Documentation, describes the required documentation to support meeting the enrollment criteria.

4.1. Inclusion Criteria

Each potential subject must satisfy all of the following criteria to be entered in the study.

1. Man or woman ≥ 18 years of age (or the legal age of consent in the jurisdiction in which the study is taking place);
2. Criterion modified per Amendment 1.
 - 2.1. Criterion modified per Amendment 2.
 - 2.2. Criterion modified per Amendment 3
 - 2.3 In Part 1, diagnosis of MDS according to WHO criteria confirmed by bone marrow aspirate and biopsy within 12 weeks prior to C1D1. A local laboratory report from this diagnostic bone marrow aspirate and biopsy must be reviewed and approved by the sponsor (Attachment 1).

In Part 2, diagnosis of MDS according to WHO criteria confirmed by bone marrow

aspirate and biopsy within 12 weeks prior to Randomization (Attachment 1). A sample of the baseline bone marrow aspirate and biopsy must be submitted to the Independent Central Pathology Reviewer for diagnostic confirmation. Central laboratory review is required to confirm diagnosis prior to Randomization.

3. IPSS low or intermediate-1 risk MDS (Attachment 3);
4. Criterion modified per Amendment 1.
 - 4.1. RBC transfusion dependent, defined as requiring at least 4 RBC units transfused over an 8-week period during the 16 weeks prior to C1D1 (Part 1) or Randomization (Part 2) (defined in Section 3.1); pre-transfusion Hb should be ≤ 9.0 g/dL to count towards the 4 units total;
5. Has MDS that is relapsed/refractory to ESA treatment; as defined by meeting any one of the criteria below:
 - 5.1. Received at least 8 weeks of treatment with a minimum weekly dose of epoetin alfa 40,000 U, epoetin beta 30,000 U or darbepoetin alfa 150 mcg (or equivalent agent/dose), without having achieved a Hb rise ≥ 1.5 g/dL or decreased RBC transfusion requirement by at least 4 units over 8 weeks
 - 5.2. Criterion 5.2 replaced by criterion 5.2.1 per Amendment 5.
 - 5.2.1 Transfusion dependence or reduction in Hb by ≥ 1.5 g/dL after hematologic improvement from at least 8 weeks of treatment with therapies outlined in inclusion criteria 5.1, in the absence of another explanation.
 - 5.3. Criterion 5.3 replaced by criterion 5.4 per Amendment 1.
 - 5.4. Endogenous serum EPO level >500 mU/mL;
6. Criterion modified per Amendment 1.
 - 6.1. Adequate iron stores, defined as transferrin saturation greater than 20% and serum ferritin greater than 400 ng/mL, measured within the screening period, or adequate iron stores as demonstrated by recent (within 12 weeks prior to C1D1 [Part 1] or Randomization [Part 2]) bone marrow examination with iron stain
7. ECOG performance status 0, 1 or 2 (Attachment 4);
8. Hematology lab test values within the following limits:
 - 8.1. ANC $\geq 1.5 \times 10^9/L$ independent of growth factor support (defined in Section 9.1.3)
 - 8.2. Platelets $\geq 75 \times 10^9/L$ independent of platelet transfusion support (defined in Section 9.1.3);
9. Biochemical laboratory test values must be within the following limits:
 - 9.1. AST, ALT and ALP ≤ 2.5 times the upper limit of normal (x ULN)
 - 9.2. Serum creatinine ≤ 2.0 x ULN
 - 9.3. Criterion 9.3 replaced by criterion 9.4 per Amendment 1.
 - 9.4. Criterion 9.4 replaced by criterion 9.4.1 per Amendment 5.
 - 9.4.1 Total bilirubin ≤ 3 x ULN (unless due to Gilbert's syndrome, ineffective erythropoiesis due to MDS, or hemolysis due to RBC transfusion) **AND**

Direct bilirubin ≤ 2 x ULN (unless due to Gilbert's syndrome, ineffective erythropoiesis due to MDS, or hemolysis due to RBC transfusion, where a direct bilirubin value of ≤ 3 x ULN or less than 1/3 of the total bilirubin value is acceptable);

- 10.1. Women of childbearing potential and practicing a highly effective method of birth control consistent with local regulations regarding the use of birth control methods for subjects participating in clinical studies: eg, established use of oral, injected or implanted hormonal methods of contraception; placement of an intrauterine device or intrauterine system; barrier methods: condom with spermicidal foam/gel/film/cream/suppository or occlusive cap (diaphragm or cervical/vault caps) with spermicidal foam/gel/film/cream/suppository; male partner sterilization (the vasectomized partner should be the sole partner for that subject); true abstinence (when this is in line with the preferred and usual lifestyle of the subject). For females, these restrictions apply for 1 month after the end of dosing. Note: If the childbearing potential changes after start of the study (eg, woman who is not heterosexually active becomes active, premenarchal woman experiences menarche) a woman must begin a highly effective method of birth control, as described above;
- 10.2. A woman of childbearing potential must have a negative serum (β -human chorionic gonadotropin [β -hCG]) or urine pregnancy test at screening and agree to be tested on Day 1 of every cycle and at end of study (30 days post last dose);
11. A man who is sexually active with a woman of childbearing potential and has not had a vasectomy must agree to use a barrier method of birth control eg, either condom with spermicidal foam/gel/film/cream/suppository or partner with occlusive cap (diaphragm or cervical/vault caps) with spermicidal foam/gel/film/cream/suppository, and all men must also not donate sperm during the study. For males, these restrictions apply for 3 months after the end of dosing.
12. Each subject (or their legally acceptable representative) must sign an informed consent form (ICF) indicating that he or she understands the purpose of and procedures required for the study and are willing to participate in the study.
13. Criterion deleted per Amendment 2.

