- Beginning at Cycle 4, collect a sample at predose Day 1 and then predose every 3 cycles (Cycles 7, 10, etc.); at the EOT visit, and at the first posttreatment visit.

Note: Ten subjects enrolled in Part 1 completed serial pharmacokinetic sampling before implementation of Amendment 2. The time points for serial PK sampling are provided in Amendment 1.

Table 3: Time and Events Schedule for Part 2 Main Study (Double-blind, Randomized 2:1, Imetelstat or Placebo Treatment)

Study Procedures	Comments	PHASE	Screening Phase	Treatment Phase (4-week cycles ± 3 days)					Posttreatment Follow-up Phase
				Up to 28 days before Randomization	Cycle 1 Day 1 (predose)	Cycle 1 Day 8, 15, 22	Cycle 2 Day 1, 8, 15, 22	Cycle 3 until EOT Day 1	
Screening									
Informed consent	Refer to Section 9.1.3 for guidance regarding COVID-19 and further clarification of screening procedures.		X						
Inclusion/exclusion criteria			X	X					
Medical history and demographics			X						
Study Medication Administration									
Randomization	Randomization will occur on C1D1 or up to 72h prior to study drug administration			X					
Dispense/administer study drug	Refers to Imetelstat or placebo (see Section 6). The screening weight is considered baseline for dose calculation. Recalculate dose if $\geq 10\%$ weight change from baseline. Dosing should begin within 72 hours of randomization in IWRS.			X		X (D1 only)	X		
Safety Assessments									
Physical exam (including weight)	Full PE at Screening; limited symptom-directed PE thereafter. Refer to Section 9.8.4 for guidance regarding COVID-19.		X	X		X (D1 only)	X	X	
Vital signs	Includes temperature, HR, SBP and DBP (preferably in a seated position). Measured and recorded prior to infusion.		X	X		X (D1 only)	X	X	
12-lead ECG	At screening, at C2D1 and as clinically indicated.		X			X (D1 only)			
Efficacy Assessments									
Transfusion history and status; myeloid growth factor treatment	Assessment of RBC transfusion requirement 16 weeks prior to Randomization and at each clinic visit until the end of treatment. Sites should make every attempt to obtain complete information, including both in-patient and out-patient transfusions (see Section 9.3.1.1 for additional information). Pre-transfusion Hb must be documented. Note: if DE Visit does not align with a Cycle Day 1 visit, then transfusion data must be collected at the DE Visit.		X	X		X (D1 only)	X	X	
								X (every 4-6 weeks) until first transfusion in Posttreatment follow-up	

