Chemistry panel for LFT investigations (local laboratory)	Includes GGT, chloride, bicarbonate, magnesium, and fractionated bilirubin. For subjects with AST, ALT, ALP or bilirubin Grade \geq 3, repeat chemistry panel and LFT investigations panel weekly until bilirubin with fractionation is $<$ 3x ULN, and AST, ALT and ALP is $<$ 5x ULN. Subjects with Grade 1 or Grade 2 elevations in AST, ALT, ALP or bilirubin at time of treatment discontinuation should continue to have tests monthly until resolution to at least baseline grade or until the start of subsequent therapy, whichever comes first.							If an adverse event of interest occurs
INR (or PT) and aPTT (local laboratory)	With additional assessments performed during treatment phase if subject has a hemorrhagic event.	X						Repeat during study if subject has a Grade \geq 3 bleeding event
Serum EPO level (local laboratory)	Only required during treatment at first suspected response. Repeat assessment is not required if response further improves.	X						At time of suspected HI-E (Hb), PR, CR

Table 3 Continued: Time and Events Schedule for Part 2, Main Study (Double-blind, Randomized 2:1, Imetelstat or Placebo Treatment)

Study Procedures	Comments	Screening Phase	Treatment Phase (4-week cycles \pm 3 days)					Posttreatment Follow-up Phase
		Up to 28 days before Randomization	Cycle 1 Day 1 (predose)	Cycle 1 Day 8, 15, 22	Cycle 2 Day 1, 8, 15, 22	Cycle 3 until EOT Day 1	EOT Visit 30 \pm 3 days after last dose	Survival Follow-up Every 12-16 weeks
Serum ferritin, transferrin saturation (local laboratory)	Total iron binding capacity and serum iron (Fe) may be performed to calculate transferrin saturation if transferrin saturation is not available at the site.	X	X		X (D1 only)	X	X	
B12 / folic acid / reticulocytes (local laboratory)		X						
Hepatitis serologies	Comprehensive hepatitis serology panel A through E. Hepatitis D serology is only required if the subject tests positive for the hepatitis B surface antigen (HBsAg). If the subject screening window is >28 days (Section 9.1.3), hepatitis screening results may still be used to determine eligibility outside of the initial 28-day screening period provided the subject is asymptomatic and does not meet Exclusion Criteria no. 12 (Section 4.2).	X						
Serum or urine pregnancy test		X			X (D1 only)	X	X	
Pharmacokinetics, Pharmacodynamics and Immunogenicity								

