- Serum chemistry ^c	10	21 ^d	210
Approximate Total			325 mL

^a. Volumes below derived for median 12 cycle duration and includes end of treatment visit.

^b. Calculated as number of samples multiplied by amount of blood per sample.

^c. Serum chemistry includes basic liver function tests. An expanded panel of liver function tests may also be required for safety reasons.

^d. Including 8 unscheduled blood samples for additional testing, if required.

Note: An indwelling intravenous cannula may be used for blood sample collection.

Repeat or unscheduled samples (including an expanded panel of liver function tests) may be taken for safety reasons or for technical issues with the samples.

Additional serum or urine pregnancy tests may be performed, at the local laboratory as determined necessary by the investigator or required by local regulation, to establish the absence of pregnancy at any time during the subject's participation in the study.

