9.1.3. Screening Phase and Predose

All subjects must sign an ICF prior to the conduct of any study-related procedures. Screening procedures other than bone marrow aspirate and biopsy will be performed up to 28 days before C1D1 (Part 1) or Randomization (Part 2) (see definition in Section 3.1).

The bone marrow aspirate and biopsy must be performed within the screening period or up to 12 weeks prior to C1D1 (Part 1) or Randomization (Part 2); however, the sample must be of adequate quality for central review. Assessments performed as part of the subject's routine clinical evaluation and not specifically for this study need not be repeated after signed ICF has been obtained provided the assessments fulfill the study requirements and are performed within the specified timeframe prior to C1D1 (Part 1) or Randomization (Part 2). Central Pathology Review (Part 2): A sample of the baseline bone marrow aspirate and biopsy must be submitted to the Independent Central Pathology Reviewer for diagnostic confirmation prior to randomization. Central laboratory review is required to confirm diagnosis of MDS prior to randomization in Part 2. Supporting laboratory samples or results (eg, historic bone marrow slides, hematology results) may be requested by the central pathologist and/or sponsor to support the screening MDS diagnosis confirmation. Central pathology laboratory diagnosis confirmation is not required for subjects participating in the Ventricular Repolarization substudy after Protocol Amendment 7.

Laboratory tests noted in the inclusion criteria must be performed and the results within the limits specified in the inclusion criteria. Limited retesting of abnormal screening values that lead to exclusion are allowed using an unscheduled visit during the screening period (to reassess eligibility). If the subject is receiving a transfusion on the same day as the screening labs, screening labs should be collected prior to transfusions. The last result obtained prior to C1D1 (Part 1) or Randomization (Part 2) will be used to determine eligibility.

- For the screening ANC to be considered growth factor independent, a 7-day period after stopping the growth factor should be observed, or 7 half-lives of growth factor used, whichever is longer. ANC should then be retested, and results must be within specified limits per inclusion criteria.

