- For the screening platelets $\geq 75 \times 10^9/L$ to be considered independent of platelet transfusion support; platelet count must be stable for 3-4 days after the transfusion. Platelets should then be retested, and results must be within specified limits.

The screening period may extend beyond 28 days upon approval from the sponsor. In these cases, all screening procedures with the exception of the ICF, will still be assessed within the protocol-specified windows prior to Randomization as described per protocol.

Prestudy transfusion history data will be collected for 16-week period prior to C1D1 (Part 1) or Randomization (Part 2). RBC transfusion requirements in the 16-week period prior to C1D1 (Part 1) or Randomization (Part 2) will be considered for the eligibility assessment.

The first QUALMS, FACT-An and EQ-5D-5L assessments will be administered prior to administration of study drug on Day 1 of Cycle 1, and before any tests, procedures, dosing or other consultations are performed, when possible (see Section 9.6).

As of Amendment 4, due to the COVID-19 pandemic all subjects in screening who have or develop clinical signs and symptoms of COVID-19 infection, if possible, should have COVID-19 testing performed according to local recommendations to assess COVID-19 status. Subjects should not be randomized under any of the following conditions:

- Subject has confirmed COVID-19 infection based on testing
- Subject has clinical signs and symptoms consistent with COVID-19 infection in the absence of testing
- Subject does not have clinical signs and symptoms consistent with COVID-19 infection but have been exposed to a person with confirmed COVID-19 infection based on testing

Enrollment can be considered after the subject has tested negative for COVID-19 infection according to local guidelines or, if testing was not performed, is asymptomatic (eg, no fever, no cough, no shortness of breath, no breathing difficulties) and it has been at least 14 days since the start of symptoms. If a subject tests positive for COVID-19 while on study, treatment may

begin/resume after 14 days from positive test and only after symptom free for at least 24 hours (smell and taste changes may linger and should not prevent from restarting treatment).

The guidance included above regarding the screening period also apply to the Ventricular Repolarization substudy.

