9.1.4. Treatment Phase

The Treatment Phase will begin on Day 1 of Cycle 1 and will continue until discontinuation of study drug.

Treatment Phase

A treatment cycle is defined as 28 days. A window of ± 3 days is allowed for visits to the clinic. Details of the procedures performed during the Treatment Phase for Part 1 and Part 2 are outlined in the Time and Events Schedules (Table 1 and Table 3). Subjects will be monitored for adverse events, laboratory abnormalities, and clinical response. All Treatment Phase visit procedures are to be done predose, unless otherwise specified, and laboratory test results must be reviewed prior to administering study drug. Adverse events and changes to concomitant medications will be recorded (see Section 11.11). Dose modifications will be made according to criteria described in Sections 6.1.1, 6.1.2, and 6.1.3. The investigator will assess subject response to therapy using the efficacy measurements and disease response criteria according to the modified IWG 2006 criteria (Attachment 5) (see Section 11.13 for adjudication of assessments by independent review).

All clinical evaluations and laboratory studies may be repeated more frequently, if clinically indicated. Note that additional weekly blood counts should be performed to follow-up any occurrence of Grade ≥ 3 thrombocytopenia or neutropenia until there is a return to baseline values. Additional coagulation testing should be performed if the subject experiences a hemorrhagic event.

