The following tests will be performed by the local laboratory at the time points shown in the Time and Events Schedule. All clinical evaluations and laboratory studies may be repeated more frequently, if clinically indicated. In some cases, if a site's local laboratory does not assess the laboratory tests noted below, other laboratory tests may be performed to calculate the values to be assessed (eg, total iron binding capacity and serum iron may be collected to calculate transferrin saturation).

- **Hematology Panel:** hemoglobin, platelet count, white blood cell count, absolute peripheral blast count, ANC

Additional weekly blood counts should be performed to follow-up any occurrence of Grade ≥ 3 thrombocytopenia or neutropenia until there is a return to baseline values.

- **Coagulation:** international normalized ratio (INR), (or prothrombin time [PT]), and activated partial thromboplastin time (aPTT)

Additional coagulation testing should be performed if the subject experiences a hemorrhagic event.

- **Serum Chemistry Panel (Routine):** sodium, potassium, blood urea nitrogen (or urea), creatinine, total bilirubin, ALT, AST, ALP, lactate dehydrogenase, and albumin. Assessment of total bilirubin with fractionation is required at screening; fractionation post-screening is also required if total bilirubin is abnormal.

Additional labs may be assessed locally to demonstrate eligibility if the subject will be enrolled with elevated bilirubin levels due to Gilbert's syndrome, ineffective erythropoiesis due to MDS, or hemolysis due to RBC transfusion.

- **Expanded Chemistry Panel for LFT Investigations:** gamma-glutamyl transpeptidase (GGT), chloride, bicarbonate, magnesium, and fractionated bilirubin required at screening for subject eligibility or as applicable for adverse event of interest.
- **Viral Hepatitis:** Screening for hepatitis will include comprehensive hepatitis serology A through E. Hepatitis D serology is only required if the subject tests positive for the hepatitis B surface antigen (HBsAg). Assessment may be performed by local or central laboratory.

- **Serum Erythropoietin**

- **Serum Ferritin, Transferrin Saturation**

Total iron binding capacity and serum iron (Fe) may be performed to calculate transferrin saturation if transferrin saturation is not available at the site.

- **Anemia Supplemental Panel:** B12, folic acid, reticulocytes

- **Pregnancy Testing:** Serum or urine pregnancy test for β -hCG

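### Inclusion 10.2 calls for a pregnancy test on Day 1 of every cycle, but Table 3 has none at Cycle 1 Day 1, so the first infusion can come up to 31 days after the last negative test

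*Protocol*

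**What the plan says.** Inclusion 10.2 (Protocol Section 4.1) asks for two things from a woman of childbearing potential: a negative serum or urine test at screening, and that she "agree to be tested on Day 1 of every cycle and at end of study (30 days post last dose".

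The row of Table 3 headed "Serum or urine pregnancy test" is marked at Screening, Cycle 2 (Day 1 only), Cycle 3 until end of treatment, and the end-of-treatment visit. The Cycle 1 Day 1 predose cell is empty.

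Section 9.8.1 includes pregnancy testing in the list it opens with "The following tests will be performed by the local laboratory at the time points shown in the Time and Events Schedule". The Schedule is therefore the document that tells a site when to test.

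Three statements fix the timing around the first dose:
- Section 9.1.3: "Screening procedures other than bone marrow aspirate and biopsy will be performed up to 28 days before" randomization in Part 2.
- Section 9.1.3, for extended screening: "all screening procedures with the exception of the ICF, will still be assessed within the protocol-specified windows prior to Randomization".
- Table 3, randomization row: "Randomization will occur on C1D1 or up to 72h prior to study drug administration".

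For the QTc substudy, inclusion 10 in Attachment 11 repeats the requirement to test on Day 1 of every cycle. The pregnancy row of Table 14 is also blank at Cycle 1 Day 1 in the text available to me.

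**The concern.** Cycle 1 is a cycle, so the criterion and the Schedule disagree about the day of first exposure. One site may follow Table 3 and not test on the first dosing day. Another may apply 10.2 literally and test. Each could claim to be following the protocol.

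Pregnancy is an exclusion (Section 4.2, no. 13) and a reason to stop study drug (Section 10.2). At a site that follows Table 3, a pregnancy arising after the screening test could be exposed to the first infusion unrecognised, and the next scheduled test is at Cycle 2 Day 1. This is a question of subject safety and of uniform conduct across sites. It does not touch the statistical inference.

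**Working it through.** **Is the blank cell genuine?** Because tables can break when text is extracted, I compared the row with its neighbours in Table 3.

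| Row in Table 3 | Screening | C1D1 | C1 D8/15/22 | Cycle 2 | Cycle 3 to EOT | EOT visit |
|---|---|---|---|---|---|---|
| Ferritin, transferrin saturation | X | X | blank | X (D1 only) | X | X |
| Pregnancy test | X | **blank** | blank | X (D1 only) | X | X |
| 12-lead ECG | X | blank | blank | X (D1 only) | blank | blank |

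The ferritin row has the same pattern apart from its mark at Cycle 1 Day 1. The ECG row, whose comment places it at screening and Cycle 2 Day 1, is likewise blank at Cycle 1 Day 1. The columns line up, so the blank is real.

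**Inputs**
- Screening window: 28 days before randomization (Section 9.1.3; Table 3 column header). It is kept when screening is extended.
- Randomization to first dose: 72 hours = 3 days (Table 3; Section 6).
- Cycle length: "A treatment cycle is defined as 28 days", with a visit window of ±3 days (Section 9.1.4).

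**Last negative test to first infusion, under Table 3**

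screening window + randomization-to-dose window = 28 + 3 = **31 days** at most.

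**Spacing of the two scheduled tests that bracket the first infusion (no dose delay)**
- 31 + 28 = **59 days**
- with the +3-day visit window: 31 + (28 + 3) = **62 days**

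**With a predose test at Cycle 1 Day 1**
- Test to first infusion: 0 days (same-day test).
- Bracketing tests: 28 days apart, or 31 with the visit window.
- Difference made by the missing cell: 59 − 28 = 31 days, or 62 − 31 = 31 days.

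**Does another provision require the test?**
- *Section 9.8.1, 5-day rule.* It says when Cycle 1 Day 1 laboratory tests need not be repeated. It follows a sentence on serum chemistry and hematology and does not name pregnancy testing, so it cannot create a test that the Schedule leaves out.
- *Section 9.1.2.* "Additional serum or urine pregnancy tests may be performed, at the local laboratory as determined necessary by the investigator" or where local regulation requires. This is permission, not a requirement.
- *Eligibility recheck at Cycle 1 Day 1 (Table 3; Section 4 note).* Section 4 relies on the last laboratory result before randomization. A negative test up to 28 days old satisfies that.
- *Contraception (inclusion 10.1).* It lowers the risk. The protocol still tests at every later cycle, so it does not treat contraception as sufficient.

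**The case against.** The strongest reply is that this is a clerical mismatch. Criterion 10.2 already states the intent, and the two texts can nearly be reconciled: the screening test covers entry and the Day 1 tests begin at Cycle 2. That reading does not fit the word every in 10.2, and it leaves a site that follows the Schedule without a test at first exposure. The blank cell changes what is done, so the point is more than wording.

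A second reply is that the other safeguards matter. Inclusion and exclusion criteria are checked again at Cycle 1 Day 1, a symptom-directed examination is scheduled that day, and the investigator may add a test at any time. This stands in part: a recheck can prompt questions or a test. Without a test, though, it cannot be relied on to show an early, unrecognised pregnancy.

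Third, the 59- and 62-day figures include the interval after the infusion, which occurs in every cycle. That is fair. The part due to the missing cell is the 31 days before dosing. That figure also equals the longest routine spacing of later Day 1 tests (28 + 3 days). The difference is that in later cycles a test falls on the dosing day itself.

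Fourth, part of the dosing wording (Section 6, and the drug-administration row of Table 3) uses should. So 31 days is the most the protocol's windows allow, and a departure from the 72-hour limit could exceed it.

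Finally, the later columns of Table 14 look shifted in extraction. That is true, and the substudy part should be confirmed against the source. The Cycle 1 Day 1 position can still be read: the ferritin row has a mark directly after Screening and the pregnancy row does not.

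**Conclusion.** The concern holds. Inclusion 10.2 and Table 3 conflict in the current text, Section 9.8.1 points sites to the table, and nothing else requires a pregnancy test before the first infusion. A site following Table 3 can dose up to 31 days after the last negative test. This assumes that both windows are used in full and that the 72-hour limit is kept.

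The reach is small. The documents give no count of women of childbearing potential, Section 1.1.3 describes MDS as a disease mainly of the elderly, and effective contraception is required at entry. Efficacy estimates, power and type I error are unaffected. This is a minor correction with a safety benefit for a few subjects.

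**What to change.** In Table 3, add a mark at Cycle 1 Day 1 (predose) to the pregnancy-test row for women of childbearing potential, and state that the negative result is reviewed before dosing. Section 9.1.4 already requires laboratory results to be reviewed before study drug is given, so no new procedure is needed.

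Make the same change in Table 14, checking its source layout while editing. It matters there also for placebo subjects who cross over: Attachment 11 restarts their assessments at Cycle 1 Day 1, so their first imetelstat infusion falls on a day with no scheduled pregnancy test. If main-study enrollment is already complete, the Table 14 change still has effect wherever substudy enrollment or crossover continues.

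The cost is one cell in each of two tables and at most one urine test per woman of childbearing potential, which 10.2 already calls for.
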